## 9.4.1.4. Final Visit/Early Termination

The following evaluations will be performed during the final visit or at early discontinuation (assessments completed at Visit 8 will not be repeated):

- Administration of CGI
- Administration of CAARS, investigator-rated version at Visits 2-8, self-rated version at Visit 8 only
- Administration of C-SSRS
- Physical examination
- ECG (12-lead)
- Vital signs and weight
- Laboratory tests (including hematology, clinical chemistry, and urinalysis)
- Urine drug screen
- Serum pregnancy test (for FOCP)
- Assessment of concomitant medications
- SM returned, assessment of compliance
- AEs assessed

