End of Study: At the end of the Visit 8 procedures or at early termination, subjects will complete end of study assessments. Subjects will return any unused capsules and undergo safety and efficacy evaluations if not already performed as part of that visit.

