# 9.1.3. End of Study Visit/Early Termination

At the end of Visit 8, or prior to early discontinuation, subjects will undergo end of study assessments. AEs will be monitored, and safety tests and efficacy scales will be administered unless assessments were performed earlier in the visit. The procedures to be performed will include physical examination, collection of vital signs, weight, ECG, blood collection for hematology and chemistry, urine collection for urinalysis, drug screen, and pregnancy test (for FOCP). Assessments of concomitant medications and SM compliance will be performed.

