### 9.4. Study Methods

### 9.4.1. Schedule of Visits and Procedures

Table 1. Schedule of Visits and Procedures presents the schedule of visits and procedures for the study.

Study Phase	Screening	Dose Treatment Period		End of Study b
	Period	(Visit window +/- 2 days)		
Activity	Visit 1 Up to 14 Days Prior to Visit 2	Visit 2	Visits 3 – 8	
Informed Consent a	Х			
Medical and Psychiatric History and Demographics	х			
Physical Exam	Х			Х
ECG (12-lead)	Х		Хc	Х
Vital Signs d	Х	Х	Х	Х
Hematology	Х			Х
Urinalysis and drug screen	Х			Х
CYP2D6 Enzyme Activity Screening	Х			
Serum Chemistry	Х			Х
Serum Pregnancy Test (for FOCP only)	х			Х
Urine Pregnancy Test (for FOCP only)		х		
CAADID	Х			
CGI	Х	Х	Х	Х
C-SSRS	Х	Х	Х	Х
CAARS e		Х	Х	Х
Concomitant Medication	Х	Х	Х	Х
Randomization		Х		
SM Dispensed		Х	Х	
SM Diary Dispensed			Xf	
Optional SM Administered On-Site g			х	
Optional PK Blood Sampling			X h	
Adverse Events			Х	Xi

a To be obtained prior to any study procedures being performed.

b To be performed at the end of Visit 8 (unless done previously during Visit 8), or at early discontinuation.

C At Visit 4 only

d Heart rate, seated blood pressure, temperature, and respiratory rate will be measured at every visit. The vital signs readings will be performed within approximately 10 minutes prior to the scheduled blood draws, where applicable. Height will be taken at screening and weight will be assessed at each visit.

e CAARS self-report done only at Visits 2 and 8, CAARS investigator-report done at Visits 2-8

 $f \qquad \mbox{At Visit 7 to record SM taken prior to Visit 8. \ \mbox{Diary to be collected at Visit 8}.$ 

- g Dose to be administered on-site after the pre-dose draw and an overnight fast at Visit 8; subjects may eat 2 hours after dosing.
- h At Visit 8, subjects who wish to participate will be dosed after an overnight fast and have a series of PK samples drawn. Samples will be taken pre-dose, and at Hours ½, 1, 2, 3, 4, 5, and 6.
- i Any subject who experiences an adverse event (whether serious or non-serious) or has a clinically significant abnormal laboratory test value(s) will be followed by the Investigator at appropriate intervals based on the severity and nature of the event, until resolved, or when the condition is assessed as stable, causality other than the SM has been found, or the subject is referred to another health care professional.

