### Clinical Global Impression (CGI)

This assessment will be administered at all study visits.

Self-rated Conners' Adult ADHD Rating Scale (CAARS) This assessment will be administered at study visits 2 and 8.

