### 3.1.3 End of Study Visit/Early Termination

At the end of Visit 8, or prior to early discontinuation, subjects will undergo end of study assessments. AEs will be monitored, and safety tests and efficacy scales will be administered unless assessments were performed earlier in the visit. Subjects will return any unused capsules and undergo safety and efficacy evaluations if not already performed as part of that visit.

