### 3.5.2 Secondary Efficacy Measures

The secondary efficacy measures are:

- Clinical Global Impression Improvement (CGI-I)
- Self-rated Conners' Adult ADHD Rating Scale (CAARS). This assessment will be administered at study Visits 2 and 8.

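### The self-rated CAARS is not scheduled at early termination, so the ITT-labelled Table 14.2.2.4 would in effect be a Visit 8 completer analysis

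*Protocol*

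**What the plan says.** **Timing of the self-rated CAARS**

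- Protocol 9.4.1.4, the list that governs both the final visit and early discontinuation: "Administration of CAARS, investigator-rated version at Visits 2-8, self-rated version at Visit 8 only".
- Table 1 footnote e, the same in Protocol 9.4.1 and SAP 3.4: "CAARS self-report done only at Visits 2 and 8, CAARS investigator-report done at Visits 2-8".
- Protocol 9.4.2, on the self-rated scale: "This assessment will be administered at study visits 2 and 8". SAP 3.5.2 repeats this.
- Protocol 9.4.1.3.1 also confines the self-rated version to Visit 8 during treatment. Protocol 9.4.1.2 lists it at baseline.

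**General wording on early termination**

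- Protocol synopsis, End of Study: "Subjects will return any unused capsules and undergo safety and efficacy evaluations if not already performed as part of that visit".
- Protocol 9.1.3: "AEs will be monitored, and safety tests and efficacy scales will be administered unless assessments were performed earlier in the visit". SAP 3.1.3 says the same.
- Table 1 marks CAARS in the End of Study column, whose footnote b reads "To be performed at the end of Visit 8 (unless done previously during Visit 8), or at early discontinuation".
- Protocol 9.4.5 and SAP 3.7 ask the investigator to try to obtain the Final Visit assessments from anyone who stops early.

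**Analysis**

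- SAP 5.3.4 compares change from baseline to Visit 8 in the self-rated score and presents it for ITT in Table 14.2.2.4.
- SAP 4.2 admits a dosed subject to ITT with a baseline and any one post-baseline efficacy assessment. It need not be a self-rating.
- SAP 5.1.6 first leaves out subjects who discontinue with no post-randomization score. For the other discontinuers it carries forward the latest available value, from planned or unplanned visits.

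**The concern.** The self-rated CAARS is the only measure of secondary endpoint 5 in Protocol 9.2, the subject's own view of benefit. The plan promises an ITT result for it and has an LOCF rule for subjects who leave. With Visit 8 as the only planned post-baseline rating, LOCF has nothing to work on for this scale. The table's title and its content would then differ, and a reader comparing it with the investigator-rated ITT tables would be comparing different sets of subjects without being told.

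Who is absent may matter. Under the protocol synopsis and 9.5.7, some subjects leave because they cannot tolerate study medication, and that can differ between arms. If leaving is related to tolerability, the comparison of those who remain could be biased; the documents do not allow its direction or size to be stated. A self-rating not taken when a subject leaves cannot be recovered afterwards.

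**Working it through.** **Step 1: what an early leaver contributes.** Take a subject who leaves after Visit 4.

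| Item | Source | Result |
|---|---|---|
| Investigator-rated CAARS | weekly, Protocol 9.4.1.3.1 | post-baseline values exist |
| CGI-I | weekly, Protocol 9.4.1.3.1 | post-baseline values exist |
| Self-rated CAARS | Visits 2 and 8, Table 1 footnote e; Visit 8 only, Protocol 9.4.1.4 | baseline only |
| ITT membership | SAP 4.2 | yes |
| Investigator-rated ITT table (14.2.1.1) | LOCF, SAP 5.1.6 | included |
| Self-rated ITT table (14.2.2.4) | no post-randomization self-rating, SAP 5.1.6 | not included |

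The exception is a self-rating that a site takes anyway, which LOCF would accept (SAP 4 and 5.1.6).

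**Step 2: reproduce the plan's figure.** Inputs from Protocol 9.2: 50 randomized, 20% dropout, 40 completers. 50 × (1 − 0.20) = 40, so the figure reproduces. Leavers: 50 × 0.20 = 10. With 1:1 allocation and an even split of leavers, 25 per arm becomes 20.

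**Step 3: ITT subjects without a post-baseline self-rating.** The documents do not say what share of leavers enters ITT, so the whole range is shown.

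| Share of the 10 leavers in ITT (assumed) | ITT size | Missing self-rating |
|---|---|---|
| all | 50 | 10/50 = 20% |
| half | 45 | 5/45 = 11% |
| none | 40 | 0/40 = 0% |

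Weekly ratings from Visit 3 make the last row unlikely, but the documents do not exclude it.

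**Step 4: precision.** For a two-sample comparison with equal variance, SE is proportional to √(1/n₁ + 1/n₂).

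- All leavers in ITT, even split: √(2/20) / √(2/25) = √(25/20) = 1.118, about 12% larger.
- Half in ITT, even split: √(45/40) = 1.061, about 6% larger.
- All 10 leavers from one arm and all in ITT, an extreme case: √(1/25 + 1/15) / √(2/25) = 1.155.

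Within each scenario the ratio is an upper bound. It assumes that every leaver would otherwise give a rating, and it counts a carried-forward value as fully informative.

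**The case against.** **The documents contradict each other.** A reader might infer that they conflict on whether the self-rating is due at early termination, so that sites could follow either version. The text does not support that:

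- Footnote e is attached to the CAARS row label, so it qualifies the End of Study mark too. The investigator-rated form alone satisfies that mark.
- The Final Visit assessments named in Protocol 9.4.5 are itemized in 9.4.1.4, the list that restricts the self-rating to Visit 8.
- The efficacy scales in Protocol 9.1.3 and SAP 3.1.3 are covered by CGI plus the investigator-rated CAARS. This wording does not exempt the self-rating, but it does not clearly require it.

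One small ambiguity remains: Visit 8 in 9.4.1.4 might loosely mean the last visit, since the same bullet keeps the Visits 2-8 range for the investigator-rated form. Footnote e favors the literal reading.

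**The SAP already covers this.** This is largely right. The first rule in SAP 5.1.6 excludes subjects without a post-randomization score, and SAP 4 lists the number of subjects among its standard statistics, so a smaller n should be visible. The exclusion is therefore not hidden. What the SAP does not say is that, for this scale, the rule removes essentially every subject who leaves before Visit 8, while the table is still called ITT.

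**Visit 8 collection fits the endpoint.** Endpoint 5 refers to perception after 5 weeks at the study dose, and a rating from someone who left earlier does not measure that. This stands as a limit on LOCF. It is the reason to show observed cases alongside, and it makes an observed-case label an acceptable alternative.

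**Conclusion.** The point holds as a minor one. On the stated schedule, an ITT subject who leaves before Visit 8 has no planned post-baseline self-rating, and Table 14.2.2.4 is in effect a Visit 8 completer analysis under an ITT label. At the protocol's assumed dropout, between 0 and 10 ITT subjects are missing, depending on how many leavers enter ITT. The corresponding loss of precision, with an even split, runs from none to about 12%. This rests on a literal reading of Visit 8 and on no site collecting the form unasked.

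A reader might go further and infer that the efficacy conclusions in general are compromised. They are not. The investigator-rated score is collected weekly and has values to carry forward. Only one secondary endpoint is touched, in a study whose sample size has no statistical basis (Protocol 9.7.2) and whose efficacy p-values are descriptive (SAP 5.1.2). Bias is a possibility, not a finding.

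**What to change.** **Preferred**

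- In Protocol 9.4.1.4, 9.4.2 and Table 1 footnote e, and in SAP 3.5.2 and Table 1 footnote e, add early termination to the self-rated CAARS schedule.
- In SAP 5.3.4, state that the existing LOCF rule applies to this scale, and show Visit 8 observed cases alongside in Table 14.2.2.4.

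**If the schedule is not changed,** or it is too late to collect the form, label Table 14.2.2.4 as Visit 8 observed cases and give n per arm.

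**Cost.** One self-report form for about 10 subjects at a visit that is already planned, one extra table panel, and a short protocol amendment. Under Protocol 10.3 the amendment needs written sponsor approval, and IRB approval too if it is judged to affect scientific quality. The analytical downside is that a carried-forward value, possibly from the starting-dose week, may not reflect 5 weeks at the study dose. LOCF does not remove dropout bias either, so the observed cases need to stand next to it. The fallback label needs only a SAP edit.

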## 9.4.2. Efficacy Assessments

*Investigator-rated Conners' Adult ADHD Rating Scale (CAARS)* This assessment will be administered at study visits 2 - 8.

### Clinical Global Impression (CGI)

This assessment will be administered at all study visits.

Self-rated Conners' Adult ADHD Rating Scale (CAARS) This assessment will be administered at study visits 2 and 8.

## 9.4.3. Pharmacokinetic Measurements

On the morning of Visit 8, all subjects who wish to participate in the optional PK day will arrive at the clinic after an overnight fast and will have all efficacy assessments administered first. The subjects then will have a pre-dose PK sample taken, and be administered either 2 x 50mg SPN-812V capsules or will be administered 1 x 50mg SPN-812V capsule for subjects who underwent dose reduction. PK sampling will occur pre-dose and at 0.5, 1, 2, 3, 4, 5, and 6 hours post-dose. Although there is a 30 minute window on draw times, efforts should be made to ensure that the time interval between any two sampling timepoints is not less than 30 minutes. Subjects may eat two hours after dosing.

SPN-812V concentrations in plasma samples will be determined by the Sponsor using a validated chromatographic method. The amount of blood to be drawn at each timepoint to determine the plasma concentrations of SPN-812V is 4mL. Information regarding sample collection, handling, and shipping procedures will be detailed in a separate manual.

Single dose administration of viloxazine hydrochloride (100mg) to ten healthy volunteers resulted in mean  $C_{max}$  near 1800 ng/mL for viloxazine at a mean  $T_{max} \sim 100$  min post-dose and with elimination half-life ~3 hr (Vandel B. et al., "Pharmacokinetics of viloxazine hydrochloride in man," European Journal of Drug Metabolism and Pharmacokinetics, 1982, Vol 7, pp. 65-68). Timepoints were chosen on the basis of these data to inform both absorption and elimination phases of the viloxazine time course while minimizing the sampling burden on patients. The design of the study provides both first-dose (in placebo group) and steady state (in active group) observations, albeit in parallel treatment groups.

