### Pharmacokinetic Sampling:

Population PK data will be pooled across all subjects who participate in this optional portion of the study. On the final visit, there is an optional PK day. All subjects who wish to participate will be dosed with active SM after an overnight fast and after all efficacy assessments are completed, Blood will be drawn for quantitative PK analysis according to the following schedule (all times +/- 30 minutes):

Pre-dose and  $\frac{1}{2}$ , 1, 2, 3, 4, 5, and 6 hours post-dose

Although draw windows are given, efforts should be made to ensure that the time interval between any two sampling timepoints is not less than 30 minutes

Drug Concentration Measurements:

The concentration of viloxazine in plasma will be determined using a validated chromatographic method.

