### 9.1.2. Dosing Period

Subjects who meet the requirements for study participation will be randomized and proceed to the Dosing Period which will last 6 weeks. Approximately 50 subjects will be randomized at a 1:1 ratio, using a centralized randomization system, to either SPN-812V or placebo. The first dose of SM should be taken the morning after the randomization visit.

At the baseline and randomization visit, baseline safety and efficacy assessments will be performed. Inclusion/Exclusion criteria should be re-assessed at this visit. Concomitant medication information will be collected. FOCP will be given a urine pregnancy test. SM will be dispensed.

Each week after randomization, subjects will return to the study site for monitoring of AEs, and the administration of safety tests and efficacy scales. Procedures to be performed are collection

CONFIDENTIAL Version 2.0

of vital signs and weight, PK blood sampling at Visit 8 (optional, if subjects wish to participate), and an ECG at Visit 4. Assessments of concomitant medications, suicide risk, and SM compliance and dispensation will be performed. Subjects who have consented to participate in the optional PK sub study will be given a diary at Visit 7 on which to record time of SM doses taken prior to Visit 8. Subjects who are participating in the optional PK sub study will be given all efficacy assessments prior to blood draws or dosing on the PK day. For subjects not participating in the optional PK sub study, their last dose will be taken the evening before the End of Study Visit (Visit 8).

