## 9.5. Treatments

#### 9.5.1. Treatments Administered

SM will be dispensed at each visit during the Randomization and Dose Treatment Periods. Subjects will receive a bottle at each visit containing the correct number of 50mg (or placebo) capsules, which is a sufficient number of capsules for dosing until the next visit. The SM will be taken by the subject orally, three times per day during waking hours, with at least 4 hours between doses (morning, noon, and evening).

At Visit 8, subjects who agree to participate in the optional PK sub study will be given 2 x 50mg SPN-812V capsules on-site in the morning, unless the subject had been down-titrated, in which case, the subject will receive 1 x 50mg SPN-812V capsule on-site in the morning. Note: all subjects who participate in the optional PK sub study will be given active SPN-812V capsule(s) in this portion. For subjects not participating in the optional PK sub study, their last dose will be taken the evening before the End of Study Visit (Visit 8).

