### 4.2 ANALYSIS POPULATIONS

The population of "All Screened Subjects" will contain all those subjects who entered the screening period to determine their eligibility to participate in the study.

The population of "All Randomized Subjects" will contain all those screened subjects who meet the requirements for study participation and are randomized, using a centralized randomization system, to either SPN-812V or placebo.

The "Intent-to-Treat (ITT) Population" consists of all randomized subjects who took at least one dose of SM, had baseline efficacy assessment and had at least one post-baseline efficacy assessment. The ITT population is the primary population for the efficacy analysis.

The "Restricted ITT Population" consists of all ITT population subjects with at least 1 efficacy assessment after three weeks of treatment.

The ITT and Restricted ITT populations will be analyzed according to treatment assigned. All subjects randomized to SPN-812V 300mg/day group, whether they are maintained on 300mg or reduced to 150mg, will be analyzed under the SPN-812V 300mg/day group.

The "Safety Population" consists of all randomized subjects who receive at least 1 dose of SM.

The PK population consists of all safety subjects who consented to participate in the optional PK sub study and had at least one evaluable (non-BLQ) PK sample drawn.

The safety and PK populations are based on actual treatment received.

Table 14.1.2 provides these analysis populations for all randomized subjects.

Listing 16.2.2 provides inclusion and exclusion criteria violations for all randomized subjects. Listing 16.2.3 gives analysis populations.

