### 6. SAFETY ANALYSES

The safety and tolerability endpoints will be summarized for the safety population according to the treatment actually received. Statistical testing will be performed for some of the safety endpoints, but the resulting p-values will be used for descriptive purposes only.

Safety will be assessed by the monitoring of AEs, vital signs, clinical laboratory tests, physical examinations, and electrocardiograms (ECG).

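### The safety analysis has no cut-off at the Visit 8 PK dose, at which placebo participants receive active SPN-812V

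*Protocol*

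**What the plan says.** **The dose.** Protocol 9.5.1 states that "all subjects who participate in the optional PK sub study will be given active SPN-812V capsule(s) in this portion". The synopsis, under pharmacokinetic sampling, says: "All subjects who wish to participate will be dosed with active SM after an overnight fast". The dose is therefore itself study medication. Protocol 9.4.3 shows that giving it to placebo subjects is deliberate: "The design of the study provides both first-dose (in placebo group) and steady state (in active group) observations, albeit in parallel treatment groups".

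**The grouping.** The safety population in SAP 4.2 "consists of all randomized subjects who receive at least 1 dose of SM". The same section adds: "The safety and PK populations are based on actual treatment received". SAP 6 repeats the rule: "The safety and tolerability endpoints will be summarized for the safety population according to the treatment actually received". The only special grouping rule, in SAP 4 and 4.2, keeps down-titrated subjects in the 300 mg/day group.

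**The window.** SAP 6.1.1 treats as treatment-emergent any AE that starts or worsens after the first study medication, and sets no end. Protocol 9.4.4.1.1 collects AEs to the end of the study. Note b to Table 1, in both documents, places the end-of-study tests at the end of Visit 8 unless they were done earlier in that visit. Note d ties vital signs to about 10 minutes before scheduled blood draws, where applicable.

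**The concern.** A placebo subject who joins the PK day has taken both treatments by the end of Visit 8. The plan groups by treatment received but does not define the term for such a subject, and it does not close the safety window at the active dose. Two tables are possible, and neither is a clean comparison of six weeks of drug with six weeks of placebo. If the subject stays under placebo, findings made under active drug are tabulated as placebo findings. If the subject moves to SPN-812V, six weeks of placebo experience are tabulated as drug experience.

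Safety against placebo is the primary objective, with only about 25 subjects per arm. Both errors tend to make the arms look more alike than they are. Efficacy is not touched: ITT subjects are analysed as assigned, and the efficacy scales precede the PK dose.

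**Working it through.** **Inputs.** About 25 randomised per arm (Protocol 9.7.2); 20% dropout and 40 completers (Protocol 9.2); six weeks of dosing (Protocol 9.1.2); PK sampling to 6 hours, with about seven hours on site (synopsis). For a single 100 mg dose, mean peak is at about 100 minutes and half-life about 3 hours (Protocol 9.4.3). PK uptake is not stated. Let m be the number of placebo subjects who take the PK dose.

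**The plan's own figure.** 50 × (1 − 0.20) = 40, which agrees with the protocol. With equal dropout (an assumption), 20 placebo subjects reach Visit 8, so m can run from 0 to about 20.

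**Reading A: the subject stays under placebo.**
- AE time: six weeks is 6 × 7 × 24 = 1,008 hours. About seven hours on the PK day is 7/1,008 = 0.7% of a participant's AE window. The share is small, but it contains the first exposure to active drug.
- End-of-study tests: the protocol allows these after the dose. Six hours after dosing is 6 − 1.67 = 4.33 hours past the mean peak, or 4.33/3 = 1.44 half-lives. On a simple log-linear decline about 2^(−1.44) = 37% of the peak remains, so the tests would be made with drug present.
- Share of placebo completers' Visit 8 values that could be affected, if all PK participants were tested after the dose: m/20, or 25% for m = 5, 50% for m = 10 and 100% for m = 20.

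**Reading B: any active dose places the whole record under SPN-812V.** The arms become 25 + m and 25 − m. If those moved carry average placebo risk, the drug-column rate is (25 × p_D + m × p_P)/(25 + m), and the difference from placebo is (p_D − p_P) × 25/(25 + m). The rates below, 40% on drug and 20% on placebo, are assumed for illustration.

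| m | Arms | Factor | Drug-column rate | Difference shown (true 20 points) |
|---|---|---|---|---|
| 0 | 25 / 25 | 1.00 | 40.0% | 20.0 |
| 5 | 30 / 20 | 0.83 | 36.7% | 16.7 |
| 10 | 35 / 15 | 0.71 | 34.3% | 14.3 |
| 20 | 45 / 5 | 0.56 | 31.1% | 11.1 |

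For example, at m = 10: (25 × 0.40 + 10 × 0.20)/35 = 12/35 = 34.3%.

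Reading B would also be selective, because only subjects who reach Visit 8 can move. Five placebo dropouts are 5/25 = 20% of the placebo column at m = 0, 5/15 = 33% at m = 10, and 5/5 at m = 20. The factor does not model this selection.

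**The case against.** A reader might infer that the SAP plans to count six weeks of placebo data under the drug arm. The documents do not support that. It needs a convention that any active dose makes a subject active, and neither document states one. Several places point the other way:

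- The primary endpoint and most of the synopsis safety analyses refer to six weeks of treatment with SPN-812V, which these subjects have not had.
- Protocol 9.4.3 still calls them the placebo group while describing their active dose.
- SAP 4.5 counts subjects as maintained on 300 mg or reduced to 150 mg, and a moved placebo subject fits neither category.
- Read that way, SAP 4.2 would put the whole PK population in one group and erase the contrast between first-dose and steady-state data.

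Grouping by treatment received is just as well explained as cover for dispensing errors. The blind data review in SAP 4.7 may still settle population definitions, the table shells are separate documents, and safety p-values are descriptive only.

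Most of this stands, and it makes reading B a worst case. It does not exclude that reading. One sentence in SAP 4.2 governs both populations, and for a correctly dosed placebo subject a measurable level in the PK data can come only from the Visit 8 dose. A single actual-treatment variable built from that sentence could carry SPN-812V into the safety tables. Nor does the objection answer reading A, which follows from the schedule and needs no assumed convention.

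**Conclusion.** The gap is real: the plan has no rule for safety data at and after an active dose that it deliberately gives to placebo subjects. The more likely result is reading A. Its effect on AE counts is probably small, about 0.7% of a participant's AE window. Its effect on final ECG, laboratory and vital-sign values could be larger, touching up to m/20 of placebo completers' Visit 8 values if the tests follow the dose.

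Reading B is possible but not the natural one. Its shrinkage factor of 25/(25+m), from 1.00 at m = 0 down to 0.56 at m = 20, is a conditional upper bound on the harm, not a forecast. The low end needs every expected placebo completer to volunteer. The figures rest on equal dropout by arm, an assumed m, average placebo risk among those moved, and illustrative AE rates. The plan should be clarified before unblinding, because either reading leaves the primary safety comparison wrongly tabulated for these subjects.

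**What to change.** In SAP 4.2, 6 and 6.1.1:

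1. Define safety treatment as the treatment received from first dose up to, but not including, the on-site PK dose at Visit 8.
2. State that the PK dose never changes a subject's safety group.
3. Report AEs that start after that dose, and ECGs, laboratory tests, vital signs and other safety measurements taken after it, separately from the six-week comparison with placebo. Apply the same cut-off to PK participants in both arms.
4. Say how an AE or test dated on the day of Visit 8 without a clock time is placed relative to the dose. SAP 6.1.1 already allows for AE onset times not being collected.

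Barring dispensing errors, this keeps the safety arms near 25 and 25 whatever the PK uptake. It costs a few sentences, one derived variable, and one extra table or listing. AE follow-up in the main comparison is slightly shorter for PK participants. A participant whose final tests were all done after the dose has no end-of-treatment value in that comparison, and the number of such subjects should be shown by arm.
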